1.5.1 Efficacy Endpoints

- OS from the time of Cycle 1, Day 1 of immunotherapy until death from any cause.
- MFS from the time of Cycle 1, Day 1 of immunotherapy until first documented distant metastases on imaging or death, whichever occurs first.
- LPFS from the time of Cycle 1, Day 1 of immunotherapy until first documented local progression on imaging or death, whichever occurs first.
- Surgical resectability determined by successful performance of resection (as defined by R0 and R1 resection).
- Pathologic response as determined by surgical margins and residual disease.

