2.2 Management of Locally Advanced Pancreatic Cancer (LAPC)

Though the treatment for LAPC consists of a combination of radiation therapy (RT) and chemotherapy, optimal treatment sequence, technique, and dosing are controversial. Chemotherapy and RT in LAPC improve local control and increase the likelihood of a margin-negative resection (ECOG 4201).³ Induction chemotherapy followed by chemoradiation results in better outcomes when compared to other treatment sequences.⁴ However, conventional external beam radiation therapy (EBRT) can take up to 6 weeks to complete, delays full-dose chemotherapy, is given with low dose chemotherapy and can lead to high rates of grade 3-4 acute toxicity (ECOG 4201 and FFCD).^{3,5}

Recent advancements in RT delivery techniques have led to increased use of stereotactic body radiation therapy (SBRT) due to its shorter duration (3-5 days), increased feasibility and established efficacy in other disease sites. Earlier studies evaluating SBRT in patients with LAPC have reported superior local control in comparison with EBRT, but resulted in high rates of grade 2-4 late GI toxicity.⁶ A prospective multicenter phase II study of SBRT in five fractions (5-6.6 Gy/fraction for a total dose of 25-33 Gy) following induction gemcitabine chemotherapy in 49 patients with LAPC was recently reported.⁷ The median OS was 13.9 months (95% CO: 10.2-16.7) and metastasis free survival was 7.7 months (95% CI: 5.8-10.2). The median local PFS was not observed and 78% were free from local progression at 1 year. Rates of acute and late grade ≥ 2 gastritis, fistula enteritis and ulcer toxicities were 2% and 11%. Five fraction SBRT not only provided superior local control, but also resulted

A Phase I/II trial of combination immunotherapy with nivolumab and a CCR2/CCR5 dual antagonist (BMS-813160) with or without GVAX following chemotherapy and radiotherapy for locally advanced pancreatic ductal adenocarcinomas (PDACs)

in a lower toxicity profile than the single fraction SBRT. There was also a significant improvement in pain scores ($p = 0.001$) and no decrease in quality of life. Studies evaluating combination chemotherapy and SBRT are ongoing. However, the addition of immunotherapy may potentially provide further benefit by additionally targeting PDAC with a completely different mechanism of action.

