10.1.2 Methods for Evaluation of Measurable Disease

All measurements should be taken and recorded in metric notation using a ruler or calipers. All baseline evaluations should be performed as closely as possible to the beginning of treatment and never more than 4 weeks before the beginning of the treatment. Subjects will be evaluated for anti-tumor effect by follow-up imaging (pancreas protocol CT, CT Chest/Abd/Pelvis, PET-CT imaging, and/or non-contrast CT chest and MRI Abd/pelvis) as outlined above. All subsequent scans (post-treatment) will be compared to the same pretreatment CT, PET/CT, or MRI that was used prior to initiating of study treatment.

The same method of assessment and the same technique should be used to characterize each identified and reported lesion at baseline and during follow-up. Imaging-based evaluation is preferred to evaluation by clinical examination unless the lesion(s) being followed cannot be imaged but are assessable by clinical exam.

Conventional CT and MRI: This guideline has defined measurability of lesions on CT scan based on the assumption that CT slice thickness is 5 mm or less. If CT scans have slice thickness greater than 5 mm, the minimum size for a measurable lesion should be twice the slice thickness. MRI is also acceptable in certain situations (e.g. for body scans).

Use of MRI remains a complex issue. MRI has excellent contrast, spatial, and temporal resolution; however, there are many image acquisition variables involved in MRI, which greatly impact image quality, lesion conspicuity, and measurement. Furthermore, the availability of MRI is variable globally. As with CT, if an MRI is performed, the technical specifications of the scanning sequences used should be optimized for the evaluation of the type and site of disease. Furthermore, as with CT, the modality used at follow-up should be the same as was used at baseline and the lesions should be measured/assessed on the same pulse sequence. Ideally, the same type of scanner should be used and the image acquisition protocol should be followed

as closely as possible to prior scans. Body scans should be performed with breath-hold scanning techniques, if possible.

10.1.3 **Metastases free survival (MFS)**

MFS is defined as the duration of time from start of treatment to identification of distant metastases on imaging or death, whichever occurs first. Individuals will be censored at the date of the last scan if no event occurs.

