10.1.4 **Overall Survival (OS)**

OS is defined as the duration of time from start of study treatment to time of death. Individuals will be censored at the date of the last scan if no event occurs.

10.1.5 **Local Progression-Free Survival (LPFS)**

LPFS is defined as the duration of time from start of treatment to time of first documented local progression or death, whichever occurs first. Individuals will be censored at the date of the last scan if no event occurs.

10.2 **Quality of Life**

Quality of life will be assessed using the European Organization for Research and Treatment in Cancer quality of life core cancer questionnaire with the pancreatic cancer module (EORTC QLQ-C30/PAN26, **Appendix D**). The EORTC QLQ-C30 is a multidimensional, 30-item questionnaire, which assesses five functional scales (physical, role, cognitive, emotional, and social), three symptom scales (fatigue, pain, and nausea/vomiting), a global health/QOL scale, as well as 6 single items.⁴³ The EORTC QLQ-PAN26 supplements the core questionnaire with 26 items specific for patients with pancreatic cancer.^{44, 45} These instruments have been validated in patients receiving treatment for metastatic and resected pancreatic cancer and are sensitive to identify treatment related changes in quality of life. We will offer subjects the option to complete their QoL questionnaires as an online REDCap survey within the 3 days prior to a visit or on paper the day of a visit. Patients who choose the online option will be sent a personalized link allowing their responses to be directly imported into our REDCap database. The REDCap database is HIPAA compliant and once survey responses are submitted, the link will no longer work and data will not be visible to the patients.

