12.6 Analysis of Secondary Endpoints – Efficacy Assessment

The secondary endpoints of interest are OS, MFS and LPFS, which are defined as the time from the study treatment initiation until death, evidence of metastatic disease or local

A Phase I/II trial of combination immunotherapy with nivolumab and a CCR2/CCR5 dual antagonist (BMS-813160) with or without GVAX following chemotherapy and radiotherapy for locally advanced pancreatic ductal adenocarcinomas (PDACs)

progression, respectively. The evaluable populations for OS, MFS and LPFS includes all subjects who receive at least one dose of study drugs (nivolumab, BMS-813160, or GVAX), and there will be a subgroup analysis for those who complete one cycle of study combination immunotherapy. If a patient is lost to follow-up, withdraws from the study or dies prior to being diagnosed with metastatic disease or local progression, or the study is ended prior to death, the patient will be considered censored at their last recorded follow-up. Kaplan-Meier survival curves will be constructed and the median survival estimates will be calculated with 95% confidence intervals using Greenwood's formula. Survival curves will be compared to historical data using log rank test. Because the study sample size is not powered for comparing the OS and MFS, comparisons with historical data will be performed for explorative purpose. Proportions of surgical resectability and pathologic response will be reported along with the corresponding binomial exact 95% confidence intervals.

Other secondary endpoints include surgical resectability and pathologic response. Surgical resectability will be determined by review of imaging and review of the subject's surgical candidacy (clinical status and tumor status) off trial after the patient completes off-trial chemotherapy and radiotherapy. Pathologic response will be graded after surgical resection or biopsy with comparisons of pre-and post-immunotherapy core biopsies or surgical samples. For each outcome, the proportion will be calculated with an exact 95% confidence interval. Individuals who drop out of the study due to treatment toxicity or other causes prior to outcome assessment will be counted as not resectable and non-responders. Logistic regression will be used to assess the impact of risk factors on each outcome. Time to event analyses will be used to assess the timing of resection and response.

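### Section 12.6 censors deaths before metastasis or local progression, contradicting the plan's own definitions of MFS and LPFS and biasing both estimates upward relative to them once such a death occurs

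*Combined protocol and SAP*

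**What the plan says.** The efficacy part of Section 1.5.1 starts both clocks at Cycle 1 Day 1. MFS runs "until first documented distant metastases on imaging or death, whichever occurs first" and LPFS "until first documented local progression on imaging or death, whichever occurs first". Sections 10.1.3 and 10.1.5 repeat this: the MFS endpoint is "identification of distant metastases on imaging or death, whichever occurs first" and the LPFS endpoint is "time of first documented local progression or death, whichever occurs first". In both, a patient is censored at the last scan only when no event has occurred.

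Section 12.6 differs in two places. It pairs OS, MFS and LPFS in order with death, metastatic disease and local progression, so death belongs to OS alone. It then lists who is censored at the last recorded follow-up: patients who are lost, who withdraw, or where the patient "dies prior to being diagnosed with metastatic disease or local progression, or the study is ended prior to death". The estimator is Kaplan-Meier, with a log-rank comparison against historical data that the section calls exploratory.

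**The concern.** The two rules estimate different quantities. Counting death gives the probability of being alive and free of metastasis (or local progression). Censoring death gives a net time to metastasis or local progression, which treats patients who died as if they had the same future risk as those still followed. Two analysts could each follow this document faithfully and report different results under the same endpoint name.

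MFS and LPFS are named secondary objectives (1.2.3 and 1.2.4). They are used again as efficacy measures in the biomarker models of Section 12.8, and MFS is used in the PD-1 correlations of Section 8.2.

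LPFS is the more exposed of the two. Metastasis ends treatment (4.9), and disease progression ends clinical follow-up (4.11.2). Survival follow-up then consists of 12-weekly contacts (4.11.3), and the schedules in Section 9 show no imaging in that column. For a patient in that phase, death may be the only LPFS event that the plan can observe, and Section 12.6 removes it.

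**Working it through.** The plan gives no event count, power or expected value for MFS or LPFS, so there is no figure to reproduce. The check compares the two rules.

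**Direction.** Kaplan-Meier multiplies (1 − events/at risk) over the event times. If a death is censored on its own date, the risk sets are unchanged and one factor below 1 is dropped. The censored curve therefore cannot lie below the composite curve, and it lies above it from the first such death.

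Small example: ten patients leave at months 2, 3, 4, 5, 6, 7, 8, 9, 10 and 12, and those at 3, 5 and 8 are deaths without progression.
- Deaths counted, just after month 9: 2/10 = 0.20.
- Deaths censored: 9/10 × 7/8 × 5/6 × 4/5 × 2/3 = 0.35.

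**Size for MFS.** Inputs: the 7.7-month median from the SBRT series in Section 2.2; constant hazards (assumed); share f of first events that are deaths (not in the documents, assumed 10% to 30%). The median with deaths censored is 7.7/(1 − f). The 12-month value is exp(−ln 2 × 12 × (1 − f)/7.7).

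| f | Median, months | 12-month value |
|---|---|---|
| deaths counted | 7.7 | 34% |
| 10%, censored | 8.6 | 38% |
| 20%, censored | 9.6 | 42% |
| 30%, censored | 11.0 | 47% |

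**Size for LPFS.** Inputs from the same series: 78% free of local progression at 1 year (taken as the net figure) and median OS 13.9 months (CI 10.2 to 16.7). Constant hazards and independence of death and local progression are assumed.
- 12-month OS = exp(−ln 2 × 12/13.9) = 0.55. Over the CI of the median it is 0.44 to 0.61.
- 12-month LPFS with deaths counted = 0.78 × 0.55 = 0.43. Over the same CI it is 0.34 to 0.47.
- With deaths censored it is 0.78, which is simply the input.
- Monthly hazards are −ln(0.78)/12 = 0.0207 for local progression and ln 2/13.9 = 0.0499 for death. The median is ln 2/0.0706 = 9.8 months with deaths counted and ln 2/0.0207 = 33.5 months with deaths censored.

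**At this trial's size.** Simulation with 10 patients (3,000 runs, 24 months of follow-up, f = 20% for MFS):

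| Mean 12-month value | Deaths counted | Censored at death | Censored at previous 12-weekly contact |
|---|---|---|---|
| MFS | 0.34 | 0.42 | 0.41 |
| LPFS | 0.43 | 0.78 | 0.77 |

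The curve censored at death was never the lower one at 12 months. The curve censored at the previous contact was lower in under 1% of runs. The two rules gave identical 12-month MFS in about 25% of runs, and identical LPFS in about 1%.

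**The case against.** The strongest reply concerns weight. Section 12.6 says that the sample size is not powered for comparing OS and MFS, and it treats the historical comparisons as exploratory. The Phase II primary endpoint is immune response, which this does not touch; nor does it touch the safety analysis or the stopping rule. That stands, and it limits the severity.

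One can also say that the upward bias is conditional. It needs at least one death without prior metastasis or local progression, and in groups of 8 to 10 there may be none for MFS. That stands too, although for LPFS it is unlikely on the illustrative inputs.

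The word for death in the censoring sentence might be a drafting slip in a sentence shared by three endpoints. But the event definitions in the same section also omit death, so the section is consistent with itself and conflicts with the others.

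A reader might infer that the rule tilts the historical comparison towards the study regimen. The documents do not support this. Of the SBRT series, Section 2.2 says: "The median local PFS was not observed and 78% were free from local progression at 1 year". In the same patients from the same starting point, an endpoint that counts death cannot have a later median than OS, which was 13.9 months. The 78% also exceeds the roughly 55% alive at 1 year computed above. Deaths were therefore probably not counted in that figure, and Section 12.6 would then be close to like-for-like with it. How the 7.7-month MFS treated deaths is not stated, and the plan does not say which dataset will supply the historical curves. The direction of bias in that comparison is unknown.

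**Conclusion.** The rule is wrong as written. Section 12.6 contradicts the event definitions in Sections 1.5.1, 10.1.3 and 10.1.5. Against those definitions it raises the Kaplan-Meier estimates once a death without the prior event occurs. The contradiction needs no assumption. The direction is exact if censoring falls on the date of death, and nearly so if it falls at an earlier contact.

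The sizes are illustrations. The MFS shift (7.7 to between 8.6 and 11.0 months) rests on constant hazards and an assumed death share. The LPFS gap (about 43% against 78% at 12 months) rests on constant hazards, independence and historical inputs. Neither forecasts this trial's results, and neither shows an advantage over historical controls. The appropriate grade is should-fix.

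**What to change.** In Section 12.6:
- Remove death from the censoring list for MFS and LPFS, and state that death from any cause is an event for both.
- Censor MFS and LPFS at the last evaluable scan in patients alive without the event. At present Sections 10.1.3 and 10.1.5 use the last scan, while 12.6 uses the last recorded follow-up.
- Censor OS at the date last known alive. Section 10.1.4 now censors OS at the last scan and should be changed to match. Survival contacts continue without scans, so censoring survivors at an old scan while counting later deaths would bias OS downward.
- For comparison with the historical 78%, report cumulative incidence of local progression with death as a competing event, as a separately named supplementary analysis.

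The cost is wording and one extra analysis, with no change to sample size or visits. MFS and LPFS estimates become less favourable. A limitation remains: local progression is not systematically observed once a patient enters survival follow-up, so the report should give the number of LPFS events that are deaths after the last scan.

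### LPFS counts death as an event in sections 1.5.1 and 10.1.5 but censors it in 12.6, and the log-rank comparison with unnamed historical data does not require one event definition on both sides

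*Combined protocol and SAP*

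**What the plan says.** Two sections define the endpoint with death as an event. Section 1.5.1 has "LPFS from the time of Cycle 1, Day 1 of immunotherapy until first documented local progression on imaging or death, whichever occurs first". Section 10.1.5 has "LPFS is defined as the duration of time from start of treatment to time of first documented local progression or death, whichever occurs first".

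Section 12.6 differs. It defines LPFS by local progression alone, and its censoring rule covers a patient who "dies prior to being diagnosed with metastatic disease or local progression": in that case "the patient will be considered censored at their last recorded follow-up". Two sentences later it states "Survival curves will be compared to historical data using log rank test".

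Objective 1.2.4 describes the LPFS controls only as a class: patients given chemotherapy and radiation alone, patients given GVAX with anti-PD-1 antibodies, or both. No study or dataset is named, and nothing says how deaths are to be coded in the controls. Section 12.6 calls comparisons with historical data exploratory.

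The one chemotherapy-plus-SBRT cohort for which the documents give local-control figures is the 49-patient multicenter study in section 2.2. Its median OS was 13.9 months (interval 10.2 to 16.7). On local control, section 2.2 reports: "The median local PFS was not observed and 78% were free from local progression at 1 year".

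**The concern.** A reader cannot tell from the documents whether a death without local progression is an LPFS event. In this population the answer largely decides the result. Patients who develop metastases stop study treatment (section 4.9). After disease progression or a new therapy, follow-up is survival contact only, with no scheduled imaging (sections 4.11.2, 4.11.3 and the schedules in section 9). Deaths without documented local progression are therefore likely.

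The historical comparison adds a second problem. If the trial counts deaths and the control does not, a cohort with the same outcomes as the control would look much worse, and a real gain in local control could be hidden. If the trial censors deaths, the curve is no longer the LPFS that sections 1.5.1 and 10.1.5 define. Kaplan-Meier then describes local progression as if patients who died could still have progressed later.

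**Working it through.** The documents give no sample size or power for LPFS, so there is no planning figure to reproduce. What can be checked is whether the passages agree, what the 78% can mean, and how much the death rule matters.

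**1. The three LPFS passages**

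| Section | Event | Death before local progression |
|---|---|---|
| 1.5.1 | local progression or death | event |
| 10.1.5 | local progression or death | event |
| 12.6 | local progression | censored |

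**2. What the 78% counted.** Inputs from section 2.2: median OS 13.9 months (10.2 to 16.7), local-PFS median not reached, 78% at one year, n = 49.

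- If every death is an event, the LPFS curve cannot lie above the OS curve, so median LPFS ≤ 13.9 months. An unreached median contradicts this, given a shared time origin and patient set (not stated in the documents).
- One-year OS under an exponential curve is 0.5^(12/median): 0.5^(12/13.9) = 0.550; 0.442 for a median of 10.2; 0.608 for 16.7.
- With less reliance on curve shape: for 10.2 months to be the lower 95% limit of the median with n = 49 and no earlier censoring, S(10.2) can be at most about 0.63 to 0.65 (linear and log-log limits). S(12) can be no higher, so this too is below 0.78.
- One-year OS of 78% with a 13.9-month median would need a Weibull shape of about 7: ln(ln 0.78 / ln 0.5) / ln(12/13.9) = 6.98. That is implausible but not impossible. The unreached median is the decisive evidence.

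**3. If sections 1.5.1 and 10.1.5 govern and the control excludes deaths.** Read the 78% as death-censored local control and take exponential, independent hazards per month.

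- Local progression: −ln(0.78)/12 = 0.0207. Death: ln 2/13.9 = 0.0499. Sum: 0.0706.
- One-year LPFS with death counted: 0.78 × 0.550 = 0.43 (0.78 × 0.442 = 0.35 to 0.78 × 0.608 = 0.47 over the OS interval). Median: ln 2/0.0706 = 9.8 months.
- Without independence, but still with exponential OS, the one-year value lies between 0.78 + 0.55 − 1 = 0.33 and 0.55.
- Event-hazard ratio from the definition alone: 0.0706/0.0207 = 3.4. Deaths make up 0.0499/0.0706 = 71% of the events.

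Under the same model, with 24 months' follow-up, no true difference and 2,000 simulated trials, deaths were counted in the trial and censored in 49 controls. A two-sided 5% log-rank test then found the trial worse in 73% of runs (n = 8), 77% (n = 10) and 82% (n = 11). With deaths censored on both sides it rejected in about 5%. The 5% two-sided level is an assumption, since 12.6 states none. The sizes follow section 12.2: 8 to 10 in Group 1; up to 10 in Group 2, whose listed parts are 6 + 5 = 11.

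**4. If section 12.6 governs.** One minus Kaplan-Meier with deaths censored gives 1 − 0.78 = 22% local progression at one year. With death competing, under the same hazards, the cumulative incidence is (0.0207/0.0706) × (1 − 0.429) = 0.168, about 17% (15.3% to 17.5% over the OS interval).

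**The case against.** A reader might infer that the planned comparison necessarily sets a death-inclusive LPFS against a death-excluding one. The documents do not support that.

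- Section 12.6, which specifies the test, censors deaths before local progression. If it governs, the trial and a death-excluding control may agree on deaths, and the gap in step 3 disappears.
- No passage makes the 49-patient study the LPFS control. It is cited as background and used gemcitabine induction, whereas this trial uses FOLFIRINOX-based induction. The controls may be GVAX plus anti-PD-1 patients instead.
- A log-rank test needs event times, which one landmark percentage and an unreached median do not supply. Controls held at patient level could be coded to either definition.

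Two further limits on the figures are fair. The 55% is an exponential-model value, not a ceiling; the less model-dependent cap is about 63% to 65%. And the text shows only that not all deaths were counted. It does not show that the 78% is a Kaplan-Meier estimate. If it were already a competing-risk figure, the cumulative incidence would be 22% and the contrast with 17% would not apply.

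Finally, the comparison is exploratory, the groups are small, and no decision rule uses LPFS.

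All of this stands, and it makes the mismatch conditional. It does not remove the contradiction between 12.6 and the two definitions, or the absence of any requirement for a common event definition.

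**Conclusion.** The concern holds in limited form. The contradiction over deaths is plain from the text and needs no assumption. That the 78% did not count all deaths is secure, given a shared time origin and patient set.

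Each reading leaves a problem. If sections 1.5.1 and 10.1.5 govern and a death-excluding control is used, the comparison is biased against the trial: about 43% against 78% at one year for identical outcomes, under exponential and independent hazards. If 12.6 governs, the reported curve is not the defined endpoint and overstates local progression, by about 5 percentage points at one year if the 78% is a death-censored Kaplan-Meier figure.

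The stakes are modest. LPFS is nonetheless a stated secondary objective with a named test, and an exploratory label does not correct a bias that comes from the definition. The change should be made, but it does not bear on the primary endpoint.

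**What to change.** In section 12.6:

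- Remove the rule that censors deaths before local progression, so that LPFS matches 1.5.1 and 10.1.5. The same sentence covers MFS, which 1.5.1 and 10.1.3 also define with death as an event, so check both endpoints together.
- Name the historical dataset for the LPFS comparison.
- Compare LPFS only with controls coded with death as an event.
- For local control, report the cumulative incidence of local progression with death as a competing event (Aalen-Johansen) in the trial, and in the controls where patient-level data allow. Gray's test can be used where both sides have such data.
- State that the 78% figure is not comparable with death-inclusive LPFS.

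The cost is SAP wording and one extra estimator, with no new trial data. The log-rank comparison of LPFS is lost wherever the controls cannot be recoded.
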